### 371 **3.5 Pump Run-in Phase Overview**

372 This phase must begin either on the same day as the final CGM run-in review visit (for participants  
373 participating in CGM run-in) or within 7 days of completion of the Screening visit (for participants  
374 skipping the CGM run-in). The purpose of the Pump Run-in phase is 1) to assess compliance with  
375 study procedures and 2) to allow the participant to transition to the study insulin pump, learn how  
376 to use it in open-loop mode, and learn infusion set care.

377 Participants will receive training on use of the study pump in open-loop mode as detailed below.

### 378 **3.6 Initiation of the Study Pump**

379 During an in-clinic visit, the study pump, associated supplies, and training will be provided to  
380 participants and the participant will be instructed to use the pump in open-loop mode in  
381 conjunction with the study CGM until the Pump Run-in review visit.

#### 382 **3.6.1 Study Pump Training**

383 Participants will receive study pump training on use of the pump in open-loop mode by a  
384 qualified trainer:

- 385 • Participants will be fully instructed on the study insulin pump. The trainer will discuss  
386 differences from the participant's personal pump, if applicable, in important aspects such  
387 as calculation of insulin on board and correction boluses and optional additional topics  
388 such as: infusion site initiation, cartridge/priming procedures, setting up the pump,  
389 charging the pump, navigation through menus, bolus procedures including stopping a  
390 bolus, etc.
- 391 • Participants will be instructed to change the study insulin pump infusion set at least once  
392 every 3 days or per manufacturer guidelines, whichever is shorter.
- 393 • Participants using bolus insulin doses at enrollment will be trained to use the pump's bolus  
394 calculator.
  - 395 ○ For subjects who may only bolus one or two meals a day, or use fixed bolus  
396 amounts as part of their prior treatment plan, they may continue to do this in the  
397 study, but they will be taught to enter the same number of units in the bolus  
398 calculator (Simplified Bolus Plan).
  - 399 ○ Additionally, it is possible during the study some subjects in the basal only group,  
400 or using simplified boluses, may realize the need to add boluses or begin using the  
401 bolus calculator, respectively. As such, they will be advanced in their bolus strategy  
402 per investigator discretion.
- 403 • The study team will assist the participant in study pump infusion site initiation and will  
404 start the participant on the study pump. The study pump will be programmed with the  
405 participant's usual basal rates and pump parameters, if applicable. The participant's  
406 personal pump, if any, will be removed.

407     • The participant will be supervised with the study pump during at least one meal or snack  
408       bolus to ensure participant understanding of the pump features.

409     • The participant will be encouraged to review the literature provided with the pump and  
410       infusion sets after the training is completed.

411     • The participant will be trained on severe hypoglycemia emergency procedures including  
412       removal of the study pump and administration of glucagon.

413     • What to do when exercising while using the system

414     • The participant will be assessed for understanding of the system interface and how to react  
415       to safety/alert messages.

416     • To prevent insulin stacking from basal insulin that is on board, participants using basal  
417       insulin at baseline will be instructed, and supervised by study staff, to set a temp basal rate  
418       to 0% that will end 24 hours after last injection of long-acting insulin, at which time the  
419       pre-programmed basal rate will be turned on. Study investigators may adjust this procedure  
420       per their usual clinical practice, and may customize this plan based on the type of basal  
421       insulin used (for example, insulin degludec with a longer half-life may require a basal rate  
422       of 50% for a second day).

423     A copy of the study pump user's guide will be provided to the participant.

#### 424       **3.6.2 Initiation of Pump by MDI Participants**

425     For MDI participants being started on the study pump, an initial basal insulin profile will be  
426       customized on a per-participant basis. Total daily insulin dose will be reduced by approximately  
427       20% as a general rule, with a recommended method outlined in a separate procedures' manual.  
428       Further adjustments to total daily dose (TDD) and intraday basal rate profile may be made during  
429       the Pump run-in period.

430     Participants will complete training on the study pump as described above, with additional  
431       emphasis on topics relevant to new pump users, such as infusion site initiation, cartridge/priming  
432       procedures, setting up the pump, charging the pump, navigation through menus, bolus  
433       procedures including stopping a bolus, etc.

434     The study team will assist the participant in study pump infusion site initiation and will start the  
435       participant on the study pump. The study pump will be programmed with the participant's insulin  
436       requirements.

#### 437       **3.6.3 System Use Guidelines**

438     The participant will be instructed to use the system in open-loop mode only.

439     Participants will be provided with sufficient supplies to last until the subsequent visit.

440     Participants will be provided with contact information and will be asked to call the study  
441       clinical staff for any health-related issues and for technical issues with the system.

442     Upon completion of the study pump training components, study staff will document, using a  
443       checklist, that the participant is familiar with the functions/features/tasks addressed during the  
444       training.

445 Participants will be provided Hyperglycemia and Hypoglycemia Guidelines during closed-loop  
446 use (section 5.2) for when their glucose levels are  $>300$  mg/dL for more than 60 minutes or  $>400$   
447 mg/dL at any time or  $<70$  mg/dL.

448 **3.7 Blood Glucose Testing**

449 Participants who skipped the CGM Run-in phase will receive supplies for blood glucose testing  
450 and blood ketone testing as described above.

451 **3.8 Assessment of Successful Completion of the Pump Run-in Phase**

452 Participants will have a follow-up visit approximately 14 days after initiation of the Pump Run-in  
453 phase to assess progress or successful completion of the phase. If needed, one or more interim  
454 visits or phone contacts may occur to assist the participant with any system use issues. Procedures  
455 will include downloading of the study pump and CGM data and the following:

- 456 • Assessment of compliance with use of the pump, including avoidance of closed-loop mode,  
457 timely cartridge and infusion set changes, and announcement of meal boluses throughout  
458 the run-in period
- 459 • Review of insulin therapy settings and adjustments to pump settings (basal rates, correction  
460 factor, insulin-to-carbohydrate ratio, etc.) or injection strategies in response to major trends  
461 observed in the CGM data
- 462 • Assessment of eligibility to continue to the main closed-loop phase of the study

463 Participants who the investigator believes may benefit from an extension of the Pump Run-in  
464 period may continue Pump Run-in for a second ~2-week period. These participants will have  
465 another follow-up visit approximately 14 days after the prior visit for a reassessment using the  
466 same procedures as described above.

467 Participants who do not meet system use compliance requirements after a second period of Pump  
468 Run-in or otherwise fail to meet study eligibility requirements will be withdrawn from the study.

469 **3.9 Optimization of Insulin Therapy**

470 Data will be obtained from CGM and/or pump downloads at the CGM and pump run-in review  
471 visit(s). Adjustments to pump settings (basal rates, correction factor, insulin-to-carbohydrate ratio,  
472 etc.) or injection strategies will be made in response to major trends observed in the CGM data,  
473 with flexibility for clinicians to adhere to guidelines and practices established at each individual  
474 practice rather than a fixed set of heuristics for all clinical centers.

475

## Chapter 4: Control-IQ (Closed-Loop) Phase

## 4.1 Control-IQ Phase Overview

478 Initiation of the Control-IQ study phase, involving use of the study pump in closed-loop mode for  
479 6 weeks, will coincide with the final Pump Run-in follow-up clinic visit described above.

480 During the Control-IQ phase, visits and contacts will be scheduled as outlined in Table 2 below:

**Table 2: Control-IQ Phase Visit and Phone Contact Schedule**

Target Day/Week	Contact Type 	Target/Allowable Window (around Target Day/Week)
3 days	P	± 2 days
1 week	P	± 2 days
2 weeks	V	± 4 days
3 weeks	P	± 4 days
6 weeks	V	± 4 days
3 days post-study	P	± 1 days
Post Exercise Challenge	C	Within 24 hours

 Contact Types are defined as Clinic Visit (V) or Phone call (P); Phone calls may be replaced by Videoconferences or Clinic Visits at investigator discretion

#### 4.1.1 Study Pump Training

485 Participants will receive instruction from a qualified trainer on use of the study pump in closed-loop  
486 mode, to include the following:

- How to turn on and off Control-IQ technology
- How to understand when Control-IQ is increasing or decreasing basal rates
- How to administer a meal or correction boluses during closed-loop system use
- What to do when exercising while using the system in closed-loop mode
- How to enable the sleep function and set the sleep schedule
- The participant will be assessed for understanding of the system interface and how to react to safety/alert messages.

Upon completion of the study pump training components, study staff will document, using a checklist, that the participant is familiar with the functions/features/tasks addressed during the training.

#### 4.1.2 System Use Guidelines

498 The participant will be instructed to use the system in closed-loop mode except if insulin is  
499 delivered by any means other than the study pump (e.g. injection of subcutaneous insulin via  
500 syringe in the event of infusion site failure). If insulin is delivered by any means other than the  
501 study pump, the participant will be instructed to turn off Control-IQ for approximately four hours.

502 The participant will also be instructed to contact study staff in case of illness with an elevated  
503 temperature >101.5 degrees Fahrenheit (38.6 degrees Celsius), other periods of significant illness,  
504 or during periods of use of medications such as epinephrine for the emergency treatment of a  
505 severe allergic reaction or asthma attack in addition to use of oral or injectable glucocorticoids to  
506 determine if closed-loop use should be temporarily discontinued.

507 Participants will be provided with sufficient supplies to last until the subsequent visit.

508 Participants will be provided with contact information and will be asked to call the study  
509 clinical staff for any health-related issues and for technical issues with the system. Participants  
510 may use the study pump without Control-IQ activated and study CGM during periods of  
511 component disconnections or technical difficulties.

512 Study staff will discuss with the participant that routine contact is required and will make  
513 arrangements for the contacts. If the participant cannot be reached, the participant's other contact  
514 methods will be utilized, including an emergency contact. Participants who are not compliant with  
515 the arranged contacts on two separate occasions may be discontinued at the discretion of the  
516 investigator.

#### 517 **4.1.3 Home Use of the Study System**

518 After training on closed-loop aspects of the study system has been completed, participants will  
519 proceed with home use (meaning free-living use at school, home, etc.) of the study pump.  
520 Participants will be asked to complete an exercise log, and use the exercise activity mode of the  
521 study pump at least once per week for a minimum of 30 minutes of exercise.

522 Follow up visits will occur per the visit listing described below. If necessary, visits should be  
523 completed out-of-window rather than missed. A visit is not considered missed until the next  
524 visit/phone window opens.

525 The goal will be for all participants to complete all scheduled visits. However, participants who  
526 (because of unforeseen circumstances or due to changes in contact precautions that may be  
527 needed during the evolving COVID-19 pandemic) are unable or unwilling to return for all  
528 follow-up visits will be permitted to return for key visits only as an alternative to withdrawal  
529 from the study. When a participant is placed into this status, missed visits will not be recorded as  
530 protocol deviations (since they would not be recorded as protocol deviations if the participant  
531 was dropped from the study).

532 Additional office visits may occur as needed.

#### 533 **Study Specific Guidance for the Exercise Challenges**

534 Study staff will review with participants that for each weekly exercise challenge, they will be  
535 required to:

- 536 1. Have extra carbohydrate containing snacks on hand during and after exercise.
- 537 2. Consider activation of exercise activity up to 45 minutes ahead of actual exercise, to allow  
538 for less insulin on board when starting exercise.
- 539 3. Consider reducing the last meal bolus prior to exercise as a way to reduce insulin on board  
540 and limit hypoglycemia.

541 4. Participants will write down the type of exercise performed, as well as the start and stop time  
542 of each exercise session on the study logbook, as this may not correlate exactly with exercise  
543 activity use on the pump.

544 5. Participants will be instructed that they may stop the exercise challenges at any point for  
545 injury or development of new symptoms (development of chest pain/pressure, feeling unwell,  
546 development of hypoglycemic symptoms, undue shortness of breath, signs of poor perfusion  
547 (leg pain/claudication), or for any other reason.

548 6. Participants will then notify the site within 24 hours after completion of each exercise  
549 challenge. The site staff will review for adverse events or new symptoms (See section 4.1.11)  
550 and review guidance on the need to stop future exercise challenges if any adverse events or  
551 new symptoms occurred per clinician judgement based on the severity of symptoms.

552 7. If a participant does not call within a week, study staff should perform an unscheduled  
553 contact to remind the participant of the required follow-up and encourage completion of the  
554 remaining exercise challenges. If a participant has to reschedule their exercise sessions, or  
555 postpone them for any reason (for example, the gym where they walk on a treadmill is too  
556 crowded and they did not want to enter to limit exposures due to COVID-19), they will be  
557 allowed to do so, and this will not be considered a protocol deviation. Similarly, if future  
558 exercise challenges are cancelled due to safety concerns, this will not be considered a  
559 protocol deviation.

560 Each clinical site can customize this guidance per their established clinical practice, to include  
561 how long to keep exercise activity active after the exercise challenge has ended.

#### 562 **4.1.4 Study Device Download**

563 Participants will be instructed to download the study CGM and pump prior to each phone contact  
564 throughout the remainder of the study.

#### 565 **4.1.5 3-Day Phone Contact**

566 Study staff will perform a phone call with the participant within 3 ( $\pm 2$ ) days following initiation  
567 of closed-loop system use.

568 The following will occur:

- 569 • Assessment of compliance with study device use by review of any available device data
- 570 • Assessment of adverse events, adverse device effects, and device issues
- 571 • Study staff will answer any questions related to device use and follow the procedure for  
572 insulin pump optimization described above if necessary.

#### 573 **4.1.6 1-Week Phone Contact**

574 Study staff will perform a phone call with the participant within 7 ( $\pm 2$ ) days following Initiation  
575 of the Control-IQ study phase.

576 The following will occur:

- 577 • Assessment of compliance with study device use by review of any available device data
- 578 • Assessment of adverse events, adverse device effects, and device issues

579     • Study staff will answer any questions related to device use and follow the procedure for  
580       insulin pump optimization described above if necessary.

581           **4.1.7 2-Week Visit**

582 Participants will have a follow-up visit 14 ( $\pm 4$ ) days from the date of initiation of closed-loop  
583 system use.

584 The participant will be offered review training to address any questions on the use of the study  
585 device including meal bolus strategies and strategies related to pump use and exercise.

586 The following will occur:

587     • Assessment of compliance with study device use by review of any available device data  
588     • Assessment of adverse events, adverse device effects, and device issues  
589     • Study staff will answer any questions related to device use and follow the procedure for  
590       insulin pump optimization described above if necessary.  
591     • Download of device data (study pump, study CGM, study BG meter) as available

592           **4.1.8 4-Week Phone Contact**

593 Study staff will perform a phone call with the participant within 28 ( $\pm 4$ ) days from the date of  
594 initiation of closed-loop system use.

595 The following will occur:

596     • Assessment of compliance with study device use by review of any available device data  
597     • Assessment of adverse events, adverse device effects, and device issues  
598     • Study staff will answer any questions related to device use and follow the procedure for  
599       insulin pump optimization described above if necessary.

600           **4.1.9 6-Week Visit**

601 All participants will have a final visit within 42 ( $\pm 4$ ) days from the date of initiation of closed-loop  
602 system use, during which the following will occur:

603     • Completion of questionnaires  
604     • Collection of exercise logbook  
605     • Weight and height measurements will be repeated  
606     • Assessment of adverse events, adverse device effects, and device issues  
607     • Download of device data (study pump, study CGM, study BG meter) as available  
608     • Study staff will supervise the participant's transition back to their prior therapy  
609       ○ Study staff will re-evaluate the subject's baseline therapy doses, noting changes in  
610        basal rates, carbohydrate ratios, and correction factors in use at the end of the  
611        trial.  
612       ○ For those subjects using basal insulin, doses will be adjusted to best match the

613 current daily insulin requirements from CSII use, typically = (total daily dose +  
614 20%)/2, with further modification as per clinical site usual practice.

615 ○ Study staff will confirm subjects have carbohydrates on hand for their drive back  
616 home, and instruct subjects to check their glucose levels when they arrive at  
617 home, prior to bedtime, and at least one time overnight on the first night to  
618 monitor for hypoglycemia, reminding subjects that insulin on board can be active  
619 for the next few hours even after stopping their pump.

620 **4.1.10 3-Day Post-Study Call**

621 All participants will have a post-study phone call 3 ( $\pm 1$ ) days after the date of their 6-Week visit  
622 and transition back to their prior insulin therapy, during which the following will occur:

623 • Check on transition back to usual home diabetes care  
624 • Assessment of adverse events

625 **4.1.11 Exercise Challenge Follow-Up**

626 Participants will be instructed to contact study staff within 24 hours of completing each exercise  
627 challenge, per guidance in section 4.1.3. The follow up call will review:

628 • The start and stop time, as well as the type of exercise performed.  
629 • Assessment of adverse events  
630 • Documentation of any safety concerns if future exercise challenges are cancelled.

631 **4.2 Early Termination Visit (If Applicable)**

632 Participants will be asked to come for an end of study visit in the event of withdrawal or early  
633 termination.

634 **4.3 Unscheduled Visits**

635 Participants may have unscheduled visits during the study period if required for additional device  
636 training or other unanticipated needs per the study investigator discretion.

637

## Chapter 5: Study Devices

638

### 5.1 Description of the Investigational Device

639

#### 5.1.1 Insulin Pump

640 The study system will include the Tandem t:slim X2 insulin pump (K201214, Tandem Diabetes  
641 Care, San Diego, CA) using firmware version 1.5.

642

#### 5.1.2 Continuous Glucose Monitoring

643 The study CGM will include Dexcom G6 transmitter and sensors. The CGM sensor will be  
644 replaced at least once every 10 days or as per manufacturer instructions.

645

#### 5.1.3 Blood Glucose Meter and Strips

646 Blood glucose levels will be measured using the study-assigned blood glucose meter  
647 (glucometer) and the CGM device will be calibrated if needed using the study glucometer and  
648 strips in accordance with the manufacturer's labeling. (Contour NEXT or Contour NEXT ONE,  
649 Ascensia Diabetes Care US, Inc., [name]).

650

#### 5.1.4 Ketone Meter

651 The study blood ketone meter is the Precision Xtra Blood Glucose and Ketone Monitoring  
652 System (Abbott Diabetes Care).

653 Blood ketone levels will be measured when needed to evaluate prolonged hyperglycemia. The  
654 blood glucose meter component of the Precision Xtra device will not be used.

655

### 5.1.5 Study Device Accountability Procedures

656 Device accountability procedures will be detailed in the site procedures manual.

657

## 5.2 Safety Measures

658

#### 5.2.1 CGM Calibration

659 Throughout the study, participants will be instructed to calibrate the study CGM in accordance  
660 with manufacturer labelling.

661

#### 5.2.2 Pump Failure

662 The study insulin pump is designed to revert to open-loop delivery of preprogrammed basal  
663 insulin levels in the event that CGM data are not available. The pump also includes various  
664 alarms and alerts to notify the user when there is a problem with insulin delivery.

665

#### 5.2.3 Hypoglycemia Threshold Alarm and Safety Protocol

666 When using the study device, hypoglycemia low threshold alerts will be set to no lower than 70  
667 mg/dL, and if a participant's CGM reading is <70 mg/dL, subjects will be instructed to treat with  
668 ~15 grams of carbohydrate and perform fingerstick testing as necessary per CGM manufacturer  
669 instructions.

670                   **5.2.4 Hyperglycemia Threshold Alarm and Safety Protocol**

671   During the course of the study, participants will be permitted to change this setting, but will be  
672   instructed to choose a value no greater than 300 mg/dL.

673   During the CGM run-in and open-loop pump wear period, if a participant's CGM reading is  
674   >300 mg/dL for over 2 hours:

- 675   • Perform a blood glucose meter check.
- 676   • For bolus insulin users, if the blood glucose is >300 mg/dL, give a correction dose of insulin  
677    if no bolus has been given within the last hour. If blood glucose does not decrease by 50  
678    mg/dL within 90 minutes of the correction dose, contact study staff for further instructions.
- 679   • For basal insulin users, contact study staff for further instructions.

680   During the time period when the closed-loop system is operational and active, if a participant's  
681   CGM reading is >300 mg/dL for over 1 hour or ≥400 mg/dL at any point, or the participant  
682   experiences severe symptoms of hyperglycemia (nausea, vomiting, abdominal pain), the  
683   participant will be instructed to take the following steps:

- 684   • Perform a blood glucose meter check.
- 685   • If the blood glucose is >300 mg/dL, check for blood ketones with the study ketone meter.
- 686   • If the ketone level is ≥ 0.6 mmol/L (or ≥ 2.5 mmol/L at any time), take correction insulin,  
687    change insulin (pump) infusion site and contact study staff. Continue to monitor their  
688    glucose and blood ketone levels until they return to normoglycemia and ketones are < 0.6  
689    mmol/l.
  - 690    ◆ If ketones are <0.6 mmol/l, they will be advised to continue to monitor their glucose  
691    until it returns to normoglycemia and to repeat the ketone measurement in 90 minutes  
692    if necessary.
  - 693    ◆ If glucose fails to correct, or symptoms persist, contact study staff immediately for  
694    further instructions, to include giving a correction dose by injection.
- 695   • If correction insulin is administered via insulin syringe, turn Control-IQ off for  
696    approximately four hours and until glucose level has returned to <180 mg/dL.
- 697   • If unable to contact study staff and the participant is vomiting, go to the Emergency  
698    Room.

699                   **5.3 Participant Access to Study Device at Study Closure**

700   Participants will be returned to their pre-study insulin therapy at the conclusion of the study and  
701   must return all study-assigned materials to the clinical site. Return of these materials must occur  
702   within 7 weeks (49 days) of initiation of closed-loop system use.

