303 Impact, Diabetes Impact, PROMISE Sleep, and System Usability total or subscale scores - a paired t-test  
304 or equivalent non-parametric test will be calculated as mentioned above for the primary outcomes.

305

306 **8. Safety Analyses**

307 All enrolled participants will be included in these analyses and all their safety events up to the final visit  
308 will be reported.

310 The circumstances of all reportable cases of the following will be summarized and tabulated by study  
311 period (run-in, OL, CLC):

312     

- Severe hypoglycemia (needing assistance)
- DKA
- Hyperosmolar Hyperglycemic Syndrome
- Serious Adverse Events
- Unanticipated adverse device effects
- Ketone events defined as a calendar day with ketone level  $>1.0$  mmol/L

313

314

315

316

317

318

319 Additionally, the number of events and the event rate per 100 person-years during CLC use will be  
320 calculated for each of the safety outcomes listed above.

321

322 **9. Device Issues**

323

324 The following tabulations and analyses will be performed to assess device issues:

325     

- Device malfunctions requiring study team contact and other reported device issues.
- Rate of different failure events and alarms per 24 hours recorded by the Control-IQ system –  
326       overall and by study week.

327

328

329

330 **10. Protocol Adherence and Retention**

331

332 The following measures of adherence will be tabulated during the 2-4 weeks of OL and during the 6  
333 weeks CLC follow-up periods:

334

- 335 • Number of protocol and procedural deviations
- 336 • Flow chart accounting for all enrolled participants up to end of study
- 337 • Flow chart of all enrolled participants at all scheduled visits and phone contacts post treatment  
initiation
- 338 • Number of and reasons for unscheduled visits and phone calls
- 339 • Number of participants who stopped OL or CLC use and reasons

340

341 **11. Intervention Adherence**

342

343 Descriptive summary statistics will be given for the percentage of time that the CLC is in active mode  
344 and the amount of CGM use over the 6-week CLC use period. A scatterplot of these two percentages  
345 will be constructed.

346

Boxplots will be given for each of these percentages for each one of the 6 weeks of follow-up.

347

Descriptive statistics will be given for the percentage of time spent in each of the CLC operational  
348 modes.

349

350 **12. Baseline Descriptive Statistics**

351

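### Open-loop pump wear has no written ketone check, and SAP 8 tabulates ketone days by period with no count of days tested and person-time for closed loop only

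*Protocol*

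**What the plan says.** Protocol 5.2.4 has two sets of steps for high glucose.

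- **Before closed loop.** The first set begins "During the CGM run-in and open-loop pump wear period, if a participant's CGM reading is" above 300 mg/dL for over 2 hours. It asks for a meter check. Bolus users whose meter value is above 300 mg/dL take a correction dose if they have had no bolus in the last hour. They call staff if glucose has not fallen by 50 mg/dL within 90 minutes. For the others: "For basal insulin users, contact study staff for further instructions". Ketones are not mentioned.
- **Closed loop.** The second set starts at CGM above 300 mg/dL for over 1 hour, at 400 mg/dL or more at any point, or with severe symptoms. After the meter check it says: "If the blood glucose is >300 mg/dL, check for blood ketones with the study ketone meter". At 0.6 mmol/L or more the participant takes correction insulin, changes the infusion site and contacts staff.

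Ketone meters are issued from run-in (3.3, 3.7). Section 3.3 ties their use to the hyperglycemia safety plan. Section 5.1.4 allows a ketone measurement when prolonged hyperglycemia calls for one, without naming a phase.

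Section 3.6.3, in the pump run-in chapter, says: "The participant will be instructed to use the system in open-loop mode only". It then hands out guidelines that it labels as being for closed-loop use, with a trigger of more than 60 minutes above 300 mg/dL, or above 400 mg/dL at any time.

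On the population, SAP 8 says: "All enrolled participants will be included in these analyses and all their safety events up to the final visit" are reported. On the layout: "The circumstances of all reportable cases of the following will be summarized and tabulated by study" period, meaning run-in, open loop (OL) and closed loop (CLC). One listed outcome is "Ketone events defined as a calendar day with ketone level" above 1.0 mmol/L. It adds: "Additionally, the number of events and the event rate per 100 person-years during CLC use will be" calculated for each listed outcome. It plans no person-time for run-in or OL, and no count of days with a ketone test in any period.

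**The concern.** There are two linked problems.

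The first is safety. Section 1.4.1.3 says ketonemia can occur when the pump or infusion set does not work properly. That hazard starts when the pump goes on, at the start of open loop. Section 2.1 asks about 3 sites for about 5 basal-only participants each, so roughly 15 people come from basal insulin alone, and 3.6.2 adds MDI users who are new to pumps. At that point the written plan gives no instruction to check ketones.

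The second is how the table reads. A ketone day can be counted only if someone tests. If the written prompt to test differs by period and the periods differ in length, three raw counts side by side do not show whether risk differs. The study's stated aims are to assess safety and to supply data for designing a larger trial, so a reader may well use this table for that purpose.

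**Working it through.** The documents give no ketone event rate and no testing frequency, so there is no planned figure to reproduce. The check is a comparison of texts, followed by the exposure arithmetic.

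**1. Steps in Protocol 5.2.4, side by side**

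| Element | CGM run-in and open loop | Closed loop |
|---|---|---|
| Duration trigger, CGM >300 mg/dL | over 2 hours | over 1 hour |
| Trigger at ≥400 mg/dL | none | yes |
| Symptom trigger | none | yes |
| Meter check | yes | yes |
| Ketone check | none | yes, if meter >300 mg/dL |
| Infusion-site change | none | yes, if ketones ≥0.6 mmol/L |
| Staff contact | basal users at once; bolus users if the correction fails | if ketones ≥0.6 mmol/L, glucose fails to correct, or symptoms persist |

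Section 3.3 does not fill the gap. It refers ketone-meter use to the safety plan, and the written plan for this phase has no ketone step.

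**2. Exposure**

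Inputs: up to 30 closed-loop starters, closed loop 6 weeks (42 days), open loop 2 to 4 weeks (14 to 28 days). Person-days = participants × days; person-years = person-days / 365.25.

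- CLC: 30 × 42 = 1,260 person-days = 3.45 person-years.
- OL, 2 weeks: 30 × 14 = 420 person-days = 1.15 person-years.
- OL, 4 weeks: 30 × 28 = 840 person-days = 2.30 person-years.
- Ratio CLC/OL: 1,260/840 = 1.5 to 1,260/420 = 3.0.

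**3. What one event means**

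Rate = 100 × events / person-years.

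- CLC: 100/3.45 = 29.0 per 100 person-years (exact Poisson 95% CI 0.7 to 161.5).
- OL: 100/2.30 = 43.5 to 100/1.15 = 87.0 per 100 person-years, with a denominator that SAP 8 does not plan to report.

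**4. How exposure and testing combine**

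Expected count = person-days × true rate × fraction detected. Assume, for illustration only, the same true rate of 1 ketone day per 100 person-days in both periods.

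- Full detection in both: CLC 12.6; OL 4.2 to 8.4. Exposure alone produces this gap.
- Half detected in OL, all in CLC: CLC 12.6; OL 2.1 to 4.2.
- Half detected in CLC, all in OL: CLC 12.6 × 0.5 = 6.3; OL 4.2 to 8.4.

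The counts cannot tell these cases apart. Person-days would remove the exposure part, and tested days would show how much ascertainment differed.

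**The case against.** The strongest reply is that open loop is not unprotected and the table is only descriptive. Basal users call staff at once, and bolus users call if the correction fails. Staff may direct a ketone test, 5.1.4 sets no phase limit, and guidance on positive ketone readings is given from run-in. Hyperglycemia or ketosis for which a participant contacts the site and receives guidance is itself reportable (7.2.4), so such calls are recorded. Stricter rules for the investigational mode are a defensible choice. SAP 8 summarizes the circumstances of cases and plans no test between periods. It limits rates to CLC for every listed outcome, and ketone events are not among the safety endpoints in Protocol 9.4.3.

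All of this stands, and it keeps the point small. It does not supply a written ketone step during pump wear, and it does not give the reader a denominator.

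Four stronger readings are tempting, and the documents do not support them:

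- **That ketones go untested in open loop.** Ad hoc and staff-directed testing is allowed.
- **That 3.6.3 proves a second, conflicting open-loop trigger.** Its sentence is labelled for closed-loop use and nearly matches the closed-loop trigger in 5.2.4, so it is probably misplaced text. It still leaves the open-loop instruction unclear.
- **That the exposure ratio could reverse, because up to 60 people may be consented.** Sixty is a cap on consent for screening. Giving all of them four weeks of open loop would require no screen failures, no run-in failures and an extension for everyone.
- **That the table will count against the device.** Closed loop has the earlier written trigger, but it may also reduce time above 300 mg/dL and so reduce prompts to test.

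**Conclusion.** The point holds as a minor one. Protocol 5.2.4 has no written ketone step for open-loop pump wear, although the meter is in hand and the risk is named. The ketone rows in SAP 8 differ between periods in the written prompt to test and in exposure, and the planned output lets a reader adjust for neither.

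The size that can be stated is exposure: a CLC/OL ratio of 1.5 to 3.0. It assumes 30 starters who each complete 42 closed-loop days and 14 to 28 open-loop days. SAP 8 covers all enrolled participants, so anyone withdrawn after pump run-in adds open-loop time that the documents do not let us estimate. The size and direction of any ascertainment bias are unknown, because testing frequency is not given.

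No efficacy conclusion changes. The stopping rule in 7.6.2 counts only serious events in participants who have started Control-IQ, so it is also unaffected.

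**What to change.** 1. **Protocol 5.2.4, open-loop block.** For participants wearing the study pump, add that a meter glucose above 300 mg/dL calls for a blood ketone check, with the same ketone actions as in closed loop. CGM run-in before pump start can stay as it is.
2. **Protocol 3.6.3.** Refer to the open-loop block of 5.2.4 in place of the closed-loop guideline.
3. **SAP 8.** For each of run-in, OL and CLC, report ketone events, participants with an event, days with a ketone test, and person-days. Add a footnote that the trigger for testing differs by period.

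One clarification helps item 3. Section 1.4.1.10 says ketone-meter data are collected, but the download lists for the 2-week and 6-week visits name only the pump, CGM and blood glucose meter. Naming the ketone meter there would remove doubt.

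The cost is a few more ketone strips and staff calls in open loop, a short protocol and handout edit, and extra columns in one table. It needs no new visits, participants or efficacy analyses.
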